In addition to therapeutic utility of acupressure, it may be cost effective by decreasing hospital stays and the need for more expensive and invasive pharmacologic interventions (9). **In this pilot feasibility study, acupressure will be used as an additional intervention to current, standard therapies.** The Near-Term Infant conceptual framework (NTI) guided the creation of our acupressure protocol to ensure incorporation of standard of care as well as optimization of acupressure elements to produce healthy outcomes in infants at risk for developing iatrogenic withdrawal syndrome. This acupressure protocol has been implemented at MCJCHV in the neonatal abstinence syndrome (NAS) population and was deemed feasible, accepted by healthcare providers and mothers, as well as safe. If proven feasible and beneficial within a PCICU population, further studies may be conducted to evaluate the efficacy of acupressure in easing with withdrawal symptoms as measured by the enhanced withdrawal assessment tool (WAT-1), when applied in conjunction with standard treatments.

Aim 1: Assess feasibility of delivering an acupressure protocol for the treatment of withdrawal in a pediatric cardiac intensive care unit. Feasibility will be assessed with successful completion of the following objectives:

- a. Achieve recruitment and consent of 4 parents per month whose infant has been exposed to opioids and/or benzodiazepines for greater than 5 days, with a retention of 80% or higher during a 24 month time period (n=40).
- b. Deliver the acupressure protocol to 20 infants at risk for developing withdrawal within the standard of care as an additional non-pharmacologic intervention (20 infants will receive standard of care).

Aim 2: Assess impact of auricular acupressure on withdrawal symptoms for an infant physically dependent on opioid and/or benzodiazepine medications. Efficacy of auricular acupressure will be assessed, in line with the standard of care, with comparison of the following assessments among intervention and control groups:

- a. Duration of opioid and/or benzodiazepine exposure
- b. Duration of wean phase
- c. Duration of mechanical ventilation
- d. Total medication dosage as measured in morphine equivalents and benzodiazepine dosages (mg/kg/patient)
- e. Hospital length of stay
- f. Severity of withdrawal symptoms as measured by the Enhanced Withdrawal Assessment Tool (WAT-1)

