- g. Presence and/or severity of delirium as measured by the Pediatric Confusion Assessment Method for the Intensive Care Unit (psCAM-ICU)
- h. Severity of agitation as measured by the Richmond Agitation Sedation Scale (RASS)
- i. Infant Pain scores as measured by Faces, Leg, Activity, Cry, Consolability Scale (FLACC)

Aim 3: Assess acceptability and implementation of the acupressure protocol as an adjunct treatment for withdrawal syndrome within the standard of care.

- a. Examine parental satisfaction of acupressure as an additional treatment as measured by the Client Satisfaction Questionnaire (CSQ8).
- b. Assess provider and staff satisfaction of acupressure as an additional therapy as measured by Acceptability of Intervention Measure (AIM), Intervention Appropriateness Measure (IAM), and Feasibility of Intervention Measure (FIM).
- c. Assess qualitative feedback as reported by parents and healthcare providers.

Impact: Results from this proposed study may expand first line, non-pharmacological therapy for infants experiencing withdrawal symptoms. Offering enhanced care for IWS infants while reducing costs related to hospital treatments is a public health concern during an opioid epidemic. Acupressure is safe, noninvasive, inexpensive, and efficiently implemented for

disorders with similar conditions to withdrawal syndrome, thus warranting additional investigation for consideration as an included standard of practice for post procedural infants.

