6.0 Study Procedures (Design)

6.1. Interventions.

Acupressure Administration (Aim1). All participants will receive the standard non-pharmacological treatment, which may include any variety of the following treatments: rooming in, soothing touch, swaddling, skin to skin, positioning, reduced stimulation, and sound machines, as needed and tolerated. These treatments are documented by nurses in the medical record. The essential characteristics for neonatal acupuncture (Figure 3) as guided by the Near-Term Infant conceptual framework (Figure 2) are included in the delivery of this acupressure protocol.

Within 24 hours of weaning medications, one of five specialty trained advanced practice providers will apply acupressure stickers to one ear (left or right depending on access to site) in accordance with the NADA protocol acupuncture technique. Application will occur at designated points including Shen Men, Liver, and Lung: in the room with the mother; and potentially during breast feeding, holding, skin to skin contact or bottle feeds. Administrators and nurses will document the activities of the infant during acupressure placement in the medical record. Stickers will remain in place for 24 hours.

At 24 hours, skin will be assessed, and stickers will then be rotated to the opposite ear every 48-72 hours if there are no adverse effects such as skin irritation. Should skin irritation be present after the 24-hour period, the sticker applied to the opposing ear will be removed in 12 hours and skin assessed. If skin irritation continues, acupressure will be discontinued, and the participant will be withdrawn from the intervention portion of the study. Parents and health care providers of the infant will still be provided surveys to assess satisfaction and acceptability of acupressure. If no skin irritation occurs, stickers may be rotated for these participants every 12 hours. Assessment of the ear skin will be documented at the time of acupressure removal in the medical record. In accordance with previous neonatal studies that applied auricular acupressure under these guidelines (48-72 hour acupressure placement), we do not anticipate skin irritation but will continue to monitor throughout hospitalization (1, 20, 28). Acupressure will be discontinued when withdrawal symptoms measure less than or equal to 3 or less than 2 above baseline with no more than 2 rescue medication doses in 24 hours. Study participants will

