receive the same assessments as non-participants and must meet the same weaning qualifications in line with the standard of care.

Acupressure Efficacy (Aim 2). As part of the standard of care, multiple metrics will be captured and compared among the intervention and control group. These include duration of opioid and/or benzodiazepine medications, duration of weaning phase, duration of mechanical ventilation, and hospital length of stay. To ensure appropriate opioid dosage comparisons, all opioid medications will be converted to morphine equivalents (mg/kg/patient); benzodiazepine medications and dosages will also be captured. Consistent with the current standard of care for infants treated in the PCICU the following assessments will be conducted: Withdrawal Assessment Tool (WAT-1) for Pediatric Withdrawal every 6 hours, Preschool Confusion Assessment Method for the ICU (psCAM-ICU) every 12 hours, Richmond Agitation-Sedation Scale (RASS) every 2-4 hours and Faces Legs Activity Cry Consolability Scale (FLACC) every 4 hours.

Acupressure Acceptability (Aim 3). Prior to discharge and after completion of the weaning protocol, parent(s) will receive the Client Satisfaction Questionnaire (CSQ8) to assess parental satisfaction of acupressure as an additional therapy. Staff and providers who cared for participants will also receive three brief electronic surveys via REDCap directly to their email prior to discharge. This survey will include 12 questions: Acceptability of Intervention Measure (AIM), Intervention Appropriateness Measure (IAM), and Feasibility of Intervention Measure (FIM) to evaluate acceptability of acupressure as a complementary therapy. Qualitative feedback back from healthcare providers and parents will be documented by administrators at time of acupressure application and skin assessment. Such feedback would include observations reported to the research team by healthcare providers or parents.

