Aim 1 Feasibility of Acupressure Protocol	Demographics: age median & interquartile range, weight median & interquartile range, % male/female, % race (black, white, Hispanic)	Duration of study
	Recruitment Metrics: % of eligible patients enrolled, % of patients prematurely terminating treatment, % of patients completing all study assessments, % of data collection procedures completed, % of missing medical record data	Duration of study
	Enrollment Metrics: % of eligible patients enrolled, % of patients prematurely terminating treatment, % of patients completing all study assessments, % of data collection procedures completed, % of missing medical record data	Duration of study

	Acupressure Administration: % sticker displacement & reapplication, adverse events Infant Activity, Non-Pharmacologic Treatments	Every 24-72 hours Every 6 hours
Aim 2 Acupressure Efficacy	Duration of Medication Exposure (days): median, interquartile range Duration of Wean Phase (days): median, interquartile range Duration of Mechanical Ventilation (days): median, interquartile range Total Medication Equivalents (mg/kg/pt): median, interquartile range Hospital Length of Stay (days): median, interquartile range Exposure to adjunct medications: median, interquartile range WAT-1 Scores: median, interquartile range psCAM-ICU Scores: median, interquartile range RASS Scores: median, interquartile range FLACC Scores: median, interquartile range	Duration of study Duration of study Duration of study Every 24 hours Duration of study Every 24 hours Every 6 hours Every 12 hours Every 2-4 hours Every 4 hours
Aim 3 Acceptability	Parental Satisfaction: CSQ8 means, SD, % scores Staff/Provider Acceptability: % AIM scores, % IAM scores, % FIM scores Qualitative Feedback	Duration of study Completion of Study Every 24-72 hours

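### Aim 3c feedback is recorded at sticker sessions, most naturally by those applying the stickers, so it risks favourable bias and has no described route for families whose sessions have stopped

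*Combined protocol and SAP*

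**What the plan says.** Aim 3c in section 2.0 is a named objective: "Assess qualitative feedback as reported by parents and healthcare providers". Section 6.1, under Acupressure Acceptability, states how this is done: "Qualitative feedback back from healthcare providers and parents will be documented by administrators at time of acupressure application and skin assessment". It adds: "Such feedback would include observations reported to the research team by healthcare providers or parents".

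Section 6.1 also says that "one of five specialty trained advanced practice providers will apply acupressure stickers to one ear", that application takes place "in the room with the mother", and that "Administrators and nurses will document the activities of the infant during acupressure placement in the medical record". The last Aim 3 row of Table 2: Assessment Measures (section 10.0) times qualitative feedback at every 24 to 72 hours.

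The other parts of Aim 3 use instruments. Parents receive the CSQ8, and staff receive the AIM, IAM and FIM by emailed REDCap survey. Section 11.0, in listing the data held, counts a qualitative item among the surveys.

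**The concern.** Acceptability comments are most useful when the person giving them can be critical at no social cost and when the record does not pass through someone with a stake in the answer. Under the method in section 6.1, a parent or nurse comments to a member of the team delivering the acupressure while the infant is still an inpatient, and that team decides what is written down. Courtesy and selective note-taking would both tend to favour the intervention.

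The second issue is timing. The occasions for documenting feedback are tied to handling the stickers. Once acupressure stops, those occasions end, and families who stopped early may have the most informative criticism. A pilot's qualitative component is there to surface such problems before a larger study. At stake is how far the 3c comments can be trusted as a guide to what needs changing.

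**Working it through.** No sample size, power or error rate bears on this point, and the plan states no figure to reproduce. The check sets the relevant sections side by side.

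**1. Who records.** The plan does not define administrators. In section 6.1 they are distinguished from nurses and are present when stickers are placed ("Administrators and nurses will document the activities of the infant during acupressure placement in the medical record"). The stickers are placed by one of five trained providers ("one of five specialty trained advanced practice providers will apply acupressure stickers to one ear"). The natural reading is that administrators are the people applying the acupressure. Section 7.0 says all study team members are trained and credentialed to apply it, so even on another reading the recorder would belong to the delivering team. Sections 7.0 and 8.0 name no independent collector.

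**2. When.** Section 6.1 names two occasions, application and skin assessment. Skin assessment is documented at removal, so it is a real second occasion. The Aim 3 time points in the Assessment Measures table read "Duration of study Completion of Study Every 24-72 hours". Matched in order to the three Aim 3 rows (parent satisfaction, staff acceptability, qualitative feedback), the 24 to 72 hour entry belongs to qualitative feedback. That is the sticker schedule, not the survey schedule.

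**3. How many infants have sessions.** Section 2.0: "Deliver the acupressure protocol to 20 infants at risk for developing withdrawal", out of 40 enrolled. 20/40 = 50%, and 40 − 20 = 20 infants have no sessions. This is expected, because those 20 do not receive the treatment being commented on.

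**4. What is left when sessions stop.**

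| Situation | Further sessions for 3c | Surveys described | Section |
|---|---|---|---|
| Acupressure continuing | Yes | CSQ8; AIM, IAM, FIM | 6.1, 10.0 |
| Stopped for persistent skin irritation | No | Still given to parents and providers | 6.1 |
| Transferred | No | Still given | 5.0 |
| Withdrawn from the study | No | CSQ8 to parents | 9.0 |

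The lack of further sessions after withdrawal is inferred from the return to standard care in section 9.0.

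**5. Whether the surveys supply qualitative content.** Section 6.1 describes the staff survey as 12 questions from the AIM, IAM and FIM. Section 10.0 reports these as frequencies and proportions, and the CSQ8 as means, standard deviations and category summaries. No open-text item is described. A low score shows that someone was dissatisfied but not why.

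**6. Section 11.0.** It lists a qualitative survey. No such instrument, recipient or time point appears in sections 6.1 or 10.0. Either a form exists and those sections omit it, or the list uses the word loosely for the session notes.

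**7. Analysis.** The Aim 3 text in section 10.0 covers only the CSQ8 and the AIM, IAM and FIM. It gives no method for summarising qualitative feedback.

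**The case against.** The strongest reply is that the plan is more open than the session schedule suggests. Section 6.1 fixes when feedback is documented, not who may give it, and the description ("Such feedback would include observations reported to the research team by healthcare providers or parents") is not limited to people at the bedside. Section 7.0 gives parents several ways to reach the principal investigator at any time and lets staff reach the team by phone. Sessions repeat, so missing one does not silence anyone. Surveys still go out after skin-irritation discontinuation and transfer, and the CSQ8 after withdrawal. Section 11.0 may already point to a qualitative form. Notes made at the time also catch practical problems that a single later question, dependent on recall, would miss.

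Much of this stands, and it rules out several stronger readings. A reader might infer that critical or absent voices are filtered out; the documents support a risk, not that outcome. A reader might infer that only people at a sticker change are heard, or that comments are taken verbally; the text says neither. A reader might also infer that the whole Aim 3 acceptability conclusion is compromised. It is not, because the Aim 3 analysis in section 10.0 rests on the rating scales.

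Three things survive. The only described way of recording 3c feedback runs through the delivering team. An open telephone line is not a stated data source, and no step is given for entering what is said on it into 3c. The instruments that reach families after sessions stop contain, as described, no free text. The value of notes made at the time is a reason to keep them, not a reason to rely on them alone.

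**Conclusion.** The concern holds as a minor one. As written, Aim 3c is at risk of courtesy bias and selective recording in the favourable direction, and the plan describes no route into 3c for the later views of families whose sessions have stopped.

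The size of the bias cannot be derived. The documents give no figure for how often parents or staff are absent from sessions, or for how many infants will stop early. The conclusion rests on two readings: that administrators are those applying the stickers, or at least members of the delivering team; and that the qualitative survey in section 11.0 is not a separate instrument already in use. If such a form exists and reaches discontinued families, most of the gap closes and what remains is to describe it.

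The effect is confined to one descriptive sub-aim. The Aim 1 benchmarks do not depend on it, nor do the CSQ8 and AIM, IAM and FIM results. The absence of sessions for the 20 standard-care infants is not a defect.

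**What to change.** - Add one open-text question to the parent form given with the CSQ8 and one to the staff REDCap survey, for example asking what worked, what did not, and whether the respondent would accept acupressure again. Include it whenever these surveys go out after discontinuation, transfer or withdrawal.
- Report those responses for Aim 3c alongside the session notes, with the two sources identified separately. The session notes need not be dropped or downgraded.
- Reconcile sections 6.1, 10.0 (Table 2: Assessment Measures) and 11.0: define administrators, and say whether a qualitative survey exists, who receives it and when. Add a sentence to the Aim 3 analysis text on how the comments will be summarised.

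The cost is one free-text item on each of two surveys already being sent, a wording change in three sections, slightly more respondent time, and some extra text to code.

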7.0 Risks to Participants

This study includes an intervention trial that requires registry in ClinicalTrials.gov. There is minimal risk to human participants in the proposed study; nonetheless, rigorous efforts will be made to protect them. We will recruit a total of 40 infants at risk for experiencing withdrawal at Monroe Carrell Jr. Children's Hospital at Vanderbilt in Nashville, TN. Recruitment and consent will be conducted by the PI and research team. Written, electronic, or telephone informed consent will be obtained prior to initiating any study activities. All key personnel and study team members are licensed healthcare professionals with extensive substance dependence and neonatal experience that have been specially trained and credentialed to apply auricular acupressure.

The only known physical risk associated with auricular acupressure is the possibility of irritation to the infant's skin such as bruising or discoloration. Skin irritation will be defined as bruising, and severe redness as documented by the acupressure provider. Should skin irritation be present after the 24-hour period of acupressure application, the sticker applied to the opposing ear will be removed in 12 hours (as this is half the initial evaluation period designated in the protocol) and skin assessed. If skin irritation occurs in the opposing ear, acupressure will be discontinued, and the participant will be withdrawn from the study. If no skin irritation occurs, stickers will be rotated for these participants every 12 hours. In accordance with previous neonatal studies, including one performed by the PI at MCJCHV, we do not anticipate skin irritation when applying auricular acupressure under these guidelines (48-72 hour acupressure placement) (1, 20, 28).

Protections for Infants. Infants in this study will be viable near term gestational age; individuals engaged in this research will have no part in determining viability of the neonate. Clinical studies have been conducted on the use of acupressure and (more invasive) acupuncture and provide data for assessing potential risks to infants. Every parent providing consent in this study will be fully informed regarding the reasonably foreseeable impact of acupressure in infants experiencing withdrawal from substances.

Adequacy of Protection Against Risks. All members of the team will have the required human participants research (CITI research ethics and compliance) and HIPPA training. All paper copies of data will be kept in a locked file cabinet in the PI's office at VUMC. Electronic

information will remain in the password protected, project number identification, REDCap database. The PI and research team will always be available to the healthcare providers and staff via cell phone. Participants' parents will be given a telephone number, pager number, and email address which will allow them to contact the PI at any time. Should there be any adverse events, PCICU providers are available to provide care for the infants.

Potential Benefits of the Proposed Research to Participants. Acupressure may serve as an additional non-pharmacologic intervention that improves symptoms of withdrawal in infants at risk of developing withdrawal syndrome. In addition to therapeutic utility of acupressure, it may be cost effective by decreasing hospital stays as well as the need for more expensive and invasive pharmacologic interventions.

Importance of the Knowledge to be Gained. Acupressure may augment current first line therapies assisting in the avoidance of medications, promoting maternal bonding, and reducing hospital length of stay. If proven feasible within a pediatric cardiac intensive care population, further studies may be conducted to evaluate the efficacy of acupressure in easing withdrawal symptoms as measured by the enhanced Withdrawal Assessment Tool (WAT), when applied in conjunction with standard treatments.

Data and Safety Monitoring Plan. The PI is responsible for the monitoring of the progress of the study and safety of all participants. Participants must meet all inclusion criteria and none of the exclusion criteria. All discussions with participants' parents will take place in confidential areas (private room or hospital room inpatient).

8.0 Reporting of Adverse Events or Unanticipated Problems involving Risk to Participants or Others

The study team is comprised of seven specialty trained and credentialed providers that will communicate any issues such as skin irritation to the PI immediately. Adverse events (AE) in this study will be minimal as there are no invasive procedures and the intervention may be administered within the standard of care as the PI has done previously at MCJCHV; with no reported AE (28). However, AE will be monitored throughout the study and any event will be followed to resolution or stabilization. An AE is defined as any unfavorable medical occurrence in a human study participant, whether or not it is considered to be related to participation in the research. Any AE will be reported to the VUMC IRB immediately. An unanticipated problem (UP) is any incident, experience, or outcome that meets all of the following criteria: a) unexpected given the research procedures and characteristics of the study population, b) related or possibly related to participation in the research and c) suggests that the research places participants or others at a greater risk of harm than was previously known or recognized. We will report any such events to the IRB. The PI will provide continuous, close monitoring of participants at VUMC with prompt reporting of AEs to the IRB and will follow VUMC reporting guidelines.

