5.0 Enrollment

A purposeful sampling technique will be utilized to recruit participants from MCJCHV as referred by healthcare providers caring for infants exposed to opioids and/or benzodiazepines for surgical procedures. Informational flyers (Appendix A) will be produced and provided by healthcare providers to parents interested in participating in the study and asked if they would like to be contacted by the PI or research team. At that time, parents may contact the PI, ask the PI to call them, or the PI will be available during the week (Monday-Friday) to discuss the study immediately following their discussion with their healthcare provider. Additionally, infants at risk for developing withdrawal may be identified by following the census in the PCICU. Daily monitoring of the PCICU census via the electronic medical record will be performed by the PI.

Previous infant studies, including a pilot feasibility study conducted by the PI at MCJCHV, have reported high retention rates of mother's that consent to acupuncture for the treatment of withdrawal but we are mindful of challenges in enrollment and retention (1, 23, 24, 28). Enrolled participants will remain in the study until cessation of opioid and/or benzodiazepine unless they are transferred to another facility (see Table 2 Exclusion Criteria) or parents voluntarily withdrawal. If an infant is transferred, acupressure will not be continued but surveys will be provided to assess satisfaction and acceptability (Aim 3). Healthcare providers will be identified through the medical record and surveys sent through their VUMC email.

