9.0 Study Withdrawal/Discontinuation

Participants may withdraw from the study at any time and continue standard care. Participants may be withdrawn if deemed medically necessary by an attending physician or study staff or if exclusion criteria are met. Participants may be withdrawn from the study by the principal investigator for repeated non-compliance. This would entail altering the seed placement for example. Participants will be reminded that participation will not affect their clinical services and the CSQ8 parental satisfaction survey will be provided to parents of participants.

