10.0 Statistical Considerations: Analysis Plan

The study sample will be characterized using descriptive statistics including mean/median, standard deviations/interquartile range, proportions and percentages as outlined below. Benchmarks for success are summarized in Table 2.

Data Analysis Aim 1. The primary goal of this aim is to assess feasibility and implementation of this study including recruitment, retention, and execution of and adherence to the acupressure protocol. Feasibility measures will be reported as frequencies and proportions (% of eligible patients enrolled, % of patients prematurely terminating treatment, % of patients completing all study assessments, % of data collection procedures completed, % of missing medical record data). Feasibility will be determined through the following benchmarks: a) recruitment success: recruitment rate of 2 infants per month over the proposed 24-month time frame (80% of 40 (ex 32) enrolled); b) study retention: retention of >80% of participants through all assessment periods, c) adherence to the acupressure administration protocol: advanced practice providers will record at least 90% of all acupressure sessions in the REDCap database and medical record.

Data Analysis Aim 2. Descriptive data will be generated for the outcomes detailed in Table 2: Aim 2 by treatment group. Given the feasibility goal of this study, we will not conduct formal statistical tests of association between the two treatment groups, but we will provide descriptives by groups and measures of variability. These statistics will inform us of data trends. Descriptives will be generated based on the intent to treat principle.

Data Analysis Aim 3. Parental satisfaction with acupressure as an additional non-pharmacologic intervention will be reported as means with standard deviations and percentiles of the CSQ8 scores within each category of the following: excellent, good, fair and poor. Provider and staff acceptability of acupressure as an additional non-pharmacologic treatment will be measured with the Acceptability of Intervention Measure (AIM), Intervention Appropriateness Measure (IAM), and Feasibility of Intervention Measure (FIM). These measures will be reported as frequency distributions and proportions (% of AIM scores, % of IAM scores, and % of FIM scores).

Table 2: Assessment Measures

Outcomes	Measures	Time Point

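### Sections 6.1 and 7.0 give conflicting consequences for repeat skin irritation: one ends the acupressure only, the other ends study participation

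*Combined protocol and SAP*

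**What the plan says.** Sections 6.1 and 7.0 describe the same course of events. Irritation is found at the 24-hour check, the sticker on the opposite ear comes off after 12 hours, and acupressure stops if that ear is also irritated. They differ on what happens to the infant next.

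- Section 6.1: "If skin irritation continues, acupressure will be discontinued, and the participant will be withdrawn from the intervention portion of the study". It adds: "Parents and health care providers of the infant will still be provided surveys to assess satisfaction and acceptability of acupressure".
- Section 7.0: "If skin irritation occurs in the opposing ear, acupressure will be discontinued, and the participant will be withdrawn from the study".

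Other text that bears on the point:

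- Section 5.0: "Enrolled participants will remain in the study until cessation of opioid and/or benzodiazepine unless they are transferred to another facility", or the parents withdraw. Section 9.0 adds further grounds, so the Section 5.0 list is not complete.
- Section 9.0 still offers the CSQ8 to parents. It does not say whether chart outcomes are collected after withdrawal.
- Section 6.1, on the Aim 2 measures: "As part of the standard of care, multiple metrics will be captured and compared among the intervention and control group".
- Section 10, Aim 1 benchmark: "retention of >80% of participants through all assessment periods". Aim 1a in Section 2.0 sets it at 80% or more of 40 infants. Section 10 also lists early termination of treatment as a percentage of its own, apart from retention.
- Section 10, Aim 2: descriptives by group under intent to treat, with no formal tests.

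**The concern.** Staff cannot follow both rules. If a case occurs, someone must decide after the event whether data collection goes on and how the infant is counted.

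Two things depend on that decision. The first is the Aim 2 description. Only the acupressure arm wears stickers, so only that arm can meet the trigger. If Section 7.0 is followed as it reads, the acupressure medians would lack later withdrawal scores, wean duration and length of stay for infants who did not tolerate the treatment. Intent to treat is meant to prevent exactly that kind of loss. The second is retention, one of the three Section 10 feasibility benchmarks. An infant withdrawn from the study would not ordinarily be described as retained through all assessment periods, whereas an infant who only stopped the stickers could be.

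**Working it through.** **Inputs from the documents.** 40 infants, randomised 1:1, 20 per arm (Sections 2.0 and 4.0). Retention must be above 80% (Section 10) or at least 80% (Aim 1a). No irritation rate or dropout rate is given.

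**The plan's own figure.** Section 10 gives 80% of 40 as 32: 0.80 × 40 = 32. This reproduces.

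**Retention limits with N = 40.**
- Above 80%: at least 33 retained, so at most L = 7 losses (33/40 = 82.5%; 32/40 = 80.0% fails).
- At least 80%: at least 32 retained, so at most L = 8 losses.

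**Cost of one case.** If Section 7.0 applies and withdrawal is counted as a loss, each case costs 1/40 = 2.5 points overall and 1/20 = 5 points in the acupressure arm. Under Section 6.1, as ordinarily read, it costs 0.

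**When the verdict changes.** Let s be the number of repeat-irritation stops and m the other losses. Section 6.1 passes if m ≤ L; Section 7.0 passes if m + s ≤ L. They disagree when L + 1 − s ≤ m ≤ L.

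| Stops s | Above 80% (L = 7) | At least 80% (L = 8) |
|---|---|---|
| 1 | m = 7 | m = 8 |
| 2 | m = 6 or 7 | m = 7 or 8 |

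Examples:
- s = 1, m = 4: 36/40 = 90% against 35/40 = 87.5%. Both pass.
- s = 2, m = 7: 33/40 = 82.5% (pass) against 31/40 = 77.5% (fail), under either wording.

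**How likely that is.** The rates here are assumptions. Take s ~ Bin(20, p) and m ~ Bin(40 − s, q), and sum the probability over the pairs where the two rules disagree.

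| Other loss q | Stop rate p | Above 80% | At least 80% |
|---|---|---|---|
| 5% | 2% | 0.15% | 0.03% |
| 5% | 5% | 0.7% | 0.2% |
| 10% | 2% | 2.4% | 1.1% |
| 10% | 5% | 7.2% | 3.6% |
| 20% | 5% | 14.9% | 15.6% |
| any | 0% | 0 | 0 |

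The chance of at least one case is 1 − (1 − p)^20: 33% at p = 2% and 64% at p = 5%. If irritation does recur at such rates, having to choose between the two rules is therefore much more likely than a changed verdict.

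**If only 32 are enrolled**, which Section 10 accepts as recruitment success, the limit is 6 losses under both wordings (26/32 = 81.25%), and one case costs 1/32, about 3.1 points.

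**The case against.** The strongest reply is that the rest of the protocol already leans towards Section 6.1. That section holds the procedures, while Section 7.0 summarises risk. Section 10 has a separate measure for stopping treatment early, which fits this event, and it applies intent to treat. The Aim 2 measures are routine chart data. Section 8.0 follows adverse events to resolution or stabilisation, and Section 9.0 still offers the CSQ8. All of this stands as evidence of intent, but no text says which rule governs, and Section 7.0 is current.

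It is also fair that the event is not expected. Sections 6.1 and 7.0 anticipate no irritation, and Sections 3.0 and 8.0 report no skin disruption in the earlier ear-seed study and no adverse events in the investigator's own work. With no formal tests, one infant's missing later data would move a median of 20 only a little. This limits the size of the effect and sets the severity.

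A reader might infer more than the documents support:

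- *That all controls are followed while acupressure infants are lost.* Controls can leave through transfer, death, worsening illness, parental withdrawal or a physician's decision (Sections 4.0, 5.0 and 9.0). Only this one reason is confined to the acupressure arm.
- *That Section 7.0 expressly makes the infant a retention loss.* It does not; that is an inference from ordinary wording.
- *That the study has no rule on data after withdrawal.* The protocol text available states none, but the consent pages were not available and could address it.
- *That Section 9.0 is a second contradiction.* It reads: "Participants may be withdrawn from the study by the principal investigator for repeated non-compliance. This would entail altering the seed placement for example". This is discretionary, the ground is general with seed placement only as an example, and it conflicts with no other section.

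**Conclusion.** The conflict is real and in current text: one event has two consequences. On its plain reading, Section 7.0 would end follow-up for infants who do not tolerate acupressure, for a reason that no control can have, contrary to the intent-to-treat descriptives in Section 10. That it would also be a retention loss is probable but not stated.

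The practical effect is small. It is zero if no repeat irritation occurs, which is what the protocol expects. Otherwise it is 2.5 points of overall retention per case with 40 enrolled. The benchmark verdict changes only if other losses already lie within a case or two of the limit. Under the assumed rates the chance of that runs from about 0.03% to 7% with 5% to 10% other loss. It reaches about 15% only if other losses are themselves near 20%, where the benchmark is in doubt anyway. Low severity: a clarification worth making, not a threat to the study's conclusions.

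**What to change.** 1. In Section 7.0, replace the ending of the sentence with the Section 6.1 consequence, so that the infant leaves the intervention part only.
2. In Section 10, state that such infants are counted in the existing percentage for early termination of treatment and not as retention losses.
3. In Section 10, state that their standard-care chart data continue to be collected and are described in the assigned arm unless the parents withdraw consent.

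No change to Section 9.0 is needed for this point. The cost is one altered phrase and a sentence or two in Section 10. No new data collection is needed, because the Aim 2 measures are already part of standard care, and the infant's protection is unchanged because the stickers come off under either rule.
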